## 2.5 Data Acquisition

Study design	2x2 factorial individually randomized controlled trial
Data source/how the data were collected	Data was be collected by a face-to-face interview at enrolment and follow-up. Data was be entered into ODK on 11 separate tablets and combined into a CSV file on a computer.

Contact information for team member responsible for data collection/acquisition	[name] [REDACTED] [name] [REDACTED] [name] [REDACTED]
Date or version (if downloaded, provide date)	
Data transfer method and date	Box
Where dataset is stored	[REDACTED]

### 3 Outcomes, Exposures, and Additional Variables of Interest

All outcomes of interest are measured at the individual level and will be aggregated by each of the four groups. Importantly, not all outcomes will be defined on all individuals because some are “conditional” outcomes e.g. conditional on having taken a test. As a consequence, although the study design is a randomized experiment, we recognize that the analysis of some outcomes may be more subject to potential confounding than that of outcomes that are defined for all individuals.

#### 3.1 Primary Outcome(s)

Outcome	Description	Variables and Source	Specifications
Testing uptake	Whether client purchases an RDT from the shop before purchasing a drug		Binary: yes/no

#### 3.2 Secondary Outcome(s)

Outcome	Description	Variables and Source	Specifications
ACT purchase among untested	Whether untested client chooses to take an ACT		Binary: yes/no
ACT purchase among test positive	Whether client chooses to take an ACT if test positive		Binary: yes/no

ACT purchase among test negative	Whether client chooses to take another drug or no drug if test negative		Binary: yes/no
Appropriate ACT use	Taking ACT if positive or not taking ACT if negative among the participants who had an RDT test		Binary: yes/no
Targeted ACT use	Taking ACT if positive or not taking ACT if negative among all participants, regardless of RDT test uptake		Binary: yes/no

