7 STATISTICAL CONSIDERATIONS

7.1 Study Outcome Measures

The primary outcome measure is the decision to purchase an RDT before purchasing a drug.

Secondary outcome measures are:

2. Decision to purchase an ACT stratified by testing status
 - a. Positive mRDT
 - b. Negative mRDT
 - c. No malaria test

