7.4 Analysis Plan

All outcomes will be binary (e.g. tested – yes/no) and will be analyzed using a modified Poisson regression model^{27,28} with log link to estimate risk ratios (RRs) and identity link to estimate risk differences (RDs) in order to provide both relative and absolute measures of intervention effect. Such an approach assumes a Poisson distribution for the binary outcome and then 'fixes' the estimated standard errors to correct for model misspecification. We minimize clustering of outcomes by outlet with highly controlled intervention delivery and careful outcome measurements by research assistants. However, to account for possible clustering due to multiple individuals being randomized within different (randomly-sampled) outlets we will use a generalized estimating equations (GEE) approach with exchangeable working covariance matrix, Kauerman-Carroll correction and robust standard errors (to correct for model misspecification due to specifying a Poisson distribution)^{29,30}. The outcome will be regressed on

2 binary indicators, one each for the higher subsidy level of the two subsidies (50% RDT subsidy and 100% ACT subsidy), together with their interaction and a vector of potential confounder variables (e.g., age, gender) to account for possible imbalances between study arms. Although we hypothesize that there will be no evidence of a (statistical) interaction (see Sample Size details above), we will test for this interaction and, if significant, will separately report the effects of each subsidy conditional on levels of the other subsidy. In the absence of an interaction, we will estimate the overall ACT subsidy effect and the overall RDT subsidy effect by taking relative contrasts from the model. All analyses will be based on the intention-to-treat principle whereby all clients will be included in the analysis irrespective of whether they complied with the intervention.

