### **1.2.2 Descriptive Analysis**

Adherence to RDT test results consists of ACT purchasing behaviors among the untested, test negative, and test positive participants. Descriptive statistics of adherence conditional on the ACT price levels (67% subsidy vs 100% subsidy) will be generated to look for possible patterns of ACT purchasing behaviors in different scenarios. We will also assess the effect of seriousness of disease and duration of symptoms on adherence to RDT test results as a sub-analysis.

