where  $Y_{ij}$  is an indicator of whether client  $j$  in outlet  $i$  ( $j=1, \dots, 84$ ;  $i = 1, \dots, 10$ ), chose to get tested for malaria in the retail outlet ( $=1$  if tested,  $0$  otherwise) and  $E(Y_{ij})$  is its expected value.  $\text{RDT\_SUBSIDY\_50\%}_{ij}$  is an indicator for whether the client received the lower RDT price of \$0.20 ( $=1$  if they received the offer of an RDT at \$0.20,  $=-1$  if they received the offer of an RDT at \$0.40) and  $\text{ACT\_SUBSIDY\_100\%}_{ij}$  is an indicator for whether the client received the higher ACT subsidy ( $=1$  if ACT price conditional on a positive test is \$0,  $=-1$  if ACT price conditional on positive test is \$0.40). Therefore,  $\text{RDT\_SUBSIDY\_50\%}_{ij} * \text{ACT\_SUBSIDY\_100\%}_{ij}$  represents an interaction term for clients who receive both the higher RDT and ACT subsidies or both the lower RDT and ACT subsidies ( $=1$  in two situations: a. RDT is offered at \$0.20 and ACT is offered at \$0 conditional on a positive test or b. RDT is offered at \$0.40 and ACT price conditional on positive test is \$0.40,  $=-1$  otherwise).  $\mathbf{w}_{ij}$  is a vector of potential confounder variables (e.g., age, gender, wealth, education) to account for possible imbalances between study arms. To account for possible clustering due to multiple individuals being randomized within 10 different (randomly-sampled) outlets we will use a generalized estimating equations (GEE) approach with

exchangeable working covariance matrix, robust standard errors (to correct for model misspecification due to specifying a Poisson distribution) and finite-sample correction (to obtain unbiased standard errors estimates using the Kauermann-Carroll method)[4, 5]. Regression diagnostics, including residual plots, will be used to verify model assumptions. Because all secondary outcomes are binary, we will use the same modelling approach to compare these outcomes.

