In the unlikely case that the modified Poisson models fail to converge, we will use a logit-link in order to estimate odds ratios as the measure of effect. As mentioned before, we will additionally provide estimates of absolute effects (risk differences) in order to provide an intuitive measure of the potential public of the interventions. Such an approach is recommended by the CONSORT statement on reporting of cluster randomized trials [6]. These risk differences will be estimated by changing the log-link to an identity link. If convergence is not achieved, we will consider an alternative specification using a normal distribution with identity link and the same approach of using robust standard errors to account for model misspecification. We will fit all models using Stata version 15 [7].

Table 3: Contrasts of interest	Population	Contrast	Alpha
Interaction effect			
(0a) The interaction effect of RDT subsidy and conditional ACT subsidy.	Full cohort	$2\beta_3$ in Model 2	0.01
Primary outcomes (given no significant interaction effect)			
(1a) Effect of RDT subsidy on the uptake of testing, averaged over the ACT price levels.	Full cohort	$2\beta_1$ in Model 1	0.02
(1b) Effect of conditional ACT subsidy on the uptake of testing, averaged over the RDT price levels.	Full cohort	$2\beta_2$ in Model 1	0.02
Primary outcomes (given strong interaction effect)			
(2a) Effect of RDT subsidy on the uptake of testing, given no conditional ACT subsidy.	No conditional ACT subsidy	$2\beta_1-2\beta_3$ in Model 1	0.01

(2b) Effect of RDT subsidy on the uptake of testing, given conditional ACT subsidy.	Conditional ACT subsidy	$2\beta_1+2\beta_3$ in Model 1	0.01
(2c) Effect of conditional ACT subsidy on the uptake of testing, given no RDT subsidy.	No RDT subsidy	$2\beta_2-2\beta_3$ in Model 1	0.01
(2d) Effect of conditional ACT subsidy on the uptake of testing, given RDT subsidy.	RDT subsidy	$2\beta_2+2\beta_3$ in Model 1	0.01

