**Table B2. Sample Means for Testing and Treating Outcomes and Behavior**

	Conditional ACT Subsidy Intervention & RDT Subsidy Intervention (A)	RDT Subsidy Intervention Only (B)	Conditional ACT Subsidy Intervention Only (C)	No Subsidy Intervention (Control) (D)	All Groups
Testing Behavior					
Had RDT					
Yes					
Positive					
ACT					
No ACT					
Negative					
ACT					
No ACT					
No					
ACT					
No ACT					

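### SAP 3.2 codes ACT purchase after a negative test in the wrong direction, and SAP 4.2 applies the between-arm model to four secondary outcomes that exist only in groups formed by testing

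*SAP*

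**What the plan says.** **Definition.** Protocol 7.1 lists the secondary outcome as "Decision to purchase an ACT stratified by testing status", with negative-test clients as one stratum, so yes means an ACT was bought. SAP 3.2 follows this for untested and test-positive clients. For the row labelled *ACT purchase among test negative* the description is "Whether client chooses to take another drug or no drug if test negative", so yes means no ACT. The remaining columns say only that the variable is binary and name no source item.

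**Analysis.** SAP 4.2 states: "Because all secondary outcomes are binary, we will use the same modelling approach to compare these outcomes". Protocol 7.4 says that all outcomes are binary "and will be analyzed using a modified Poisson regression model", with both subsidy indicators in the model. Elsewhere the SAP leans the other way:

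- Section 1.2.2 promises "Descriptive statistics of adherence conditional on the ACT price levels".
- Section 3 warns that "the analysis of some outcomes may be more subject to potential confounding than that of outcomes that are defined for all individuals", but gives no remedy.
- Table 3 lists contrasts for testing uptake only, for example "Effect of RDT subsidy on the uptake of testing, averaged over the ACT price levels". Shell B3 is also limited to testing.
- Shell B2, titled "Sample Means for Testing and Treating Outcomes and Behavior", shows ACT and no ACT by test result as sample means.

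**The concern.** An analyst cannot follow all of these passages.

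**Direction.** The RR is the primary effect measure, and recoding a binary outcome to its complement does not give the reciprocal RR. An analyst who follows the description produces a valid RR for non-purchase, which would then be reported under a label that says purchase.

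**Comparability.** Randomisation makes arms comparable when everyone randomised is counted. Testing happens after randomisation, and the trial's hypothesis is that price changes who tests. Clients who test only because of a higher subsidy move from the untested group in one arm to the tested group in another. A modelled RR inside those groups could be read as a price effect on ACT purchase when part of it reflects who chose to test. Untested and test-negative clients pay the unsubsidised ACT price in every arm, so an ACT-factor RR among them cannot come from a different ACT price paid. It could reflect selection or a reaction to the offer.

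**Two smaller points.** Protocol section 4 counts a negative client as adherent if they use another drug, whereas SAP *Appropriate ACT use* counts any negative client who takes no ACT. The two disagree on a negative client who buys nothing, which questionnaire item 5.1 records as code 7. *Targeted ACT use* covers all participants but does not say how untested clients are scored; no is the natural reading.

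**Working it through.** **Planned figures.** Uptake (SAP Table 1) is A 85% (RDT 50%, ACT 100%), B 75% (RDT 50%, ACT 67%), C 70% (RDT 0%, ACT 100%) and D 60% (RDT 0%, ACT 67%). The marginal rates behind the sample size reproduce closely. With n per level = [1.960·√(2p̄q̄) + 1.282·√(p₁q₁+p₂q₂)]² / (p₁−p₂)²:

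- ACT, 67.5% vs 77.5%: 417 per level, 834 in total (plan 838).
- RDT, 65% vs 80%: 185 per level, 370 in total (plan 374).

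With 210 per arm, expected untested counts are A 31.5, B 52.5, C 63 and D 84, or 231 of 840.

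**Direction of coding.** Assume 20% vs 30% buy an ACT after a negative test. As labelled, RR = 0.20/0.30 = 0.67. As described, RR = 0.80/0.70 = 1.14. The reciprocal of 0.67 would be 1.50. The risk difference only changes sign.

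**Composition of the groups.** Assume a higher subsidy never deters testing. Per 100 clients there are then 60 always-testers, 25 induced testers (who test only at some higher subsidy) and 15 never-testers.

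| Arm | Induced share of tested | Induced share of untested |
|---|---|---|
| A | 25/85 = 29.4% | 0/15 = 0% |
| B | 15/75 = 20.0% | 10/25 = 40% |
| C | 10/70 = 14.3% | 15/30 = 50% |
| D | 0/60 = 0% | 25/40 = 62.5% |

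Pooled to the planned main effects, higher vs lower subsidy:

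- Tested, ACT factor: (25+10)/155 = 23% vs 15/135 = 11%.
- Tested, RDT factor: 40/160 = 25% vs 10/130 = 8%.
- Untested, ACT factor: 15/45 = 33% vs 35/65 = 54%.
- Untested, RDT factor: 10/40 = 25% vs 40/70 = 57%.

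**RRs with no true price effect.** Following the 2β contrasts in SAP Table 3, the ACT RR is √(A/B × C/D) and the RDT RR is √(A/C × B/D), where the letters now stand for outcome rates. Purchase rates by client type are assumed. Only the range after a negative test has a source: Protocol 2.1 cites 1–40%.

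| Group | Assumed rates | ACT RR | RDT RR |
|---|---|---|---|
| Test-negative, always/induced | 20%/10% | 0.94 | 0.91 |
| Test-negative | 20%/20% | 1.00 | 1.00 |
| Test-negative | 20%/30% | 1.06 | 1.09 |
| Test-negative | 40%/10% | 0.90 | 0.86 |
| Untested, never/induced | 60%/50% | 1.05 | 1.07 |
| Untested | 70%/40% | 1.14 | 1.20 |
| Untested | 40%/70% | 0.85 | 0.80 |
| Untested | equal | 1.00 | 1.00 |

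For example, untested at 70%/40% has arm rates A 0.700, B 0.580, C 0.550 and D 0.5125. The ACT RR is √(0.700/0.580 × 0.550/0.5125) = 1.14. The test-negative rows assume equal malaria positivity across client types. On the SAP's non-purchase coding, the 20%/10% row becomes 1.01 and 1.02.

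**Appropriate ACT use.** Let client types behave alike but differ in positivity (40%/20% or 20%/40%), with 30% taking an ACT if positive and 1% if negative. The RRs are 1.02 and 1.03, or 0.98 and 0.97. With 70% and 20% they are within 0.5% of 1.00. The bias is small in these cases.

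**Targeted ACT use with untested scored no.** If appropriate use among tested clients is constant, that rate cancels and the RR equals the uptake RR: √(85/75 × 70/60) = 1.15 for ACT and √(85/70 × 75/60) = 1.23 for RDT.

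**The case against.** Much of the SAP already treats these outcomes with care. Section 3 concedes confounding, section 1.2.2 makes adherence descriptive, and no alpha, power or decision rule rests on these RRs. Shell B2 shows both ACT and no ACT after a negative test, so either coding can be recovered. This limits the damage, but neither section overrides the SAP 4.2 instruction to model every secondary outcome, and shell B2 does not fix the direction of a modelled RR.

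The illustrated biases also sit within sampling error. For the untested RDT contrast (84 vs 147 clients, an assumed 55% purchase, clustering ignored), the 95% limits are a factor of exp[1.96·√(0.45/0.55 × (1/84 + 1/147))] = 1.27 either way. That stands: the bias may not be detectable in this trial. It would still shift the estimate.

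The arm A against arm D shares are the extremes, and Table 3 contains no such contrast. The pooled shares are milder, and the illustrative RRs already average over the arms as the planned contrasts do. The illustrations are unadjusted, whereas the model carries age, gender, wealth and education. Adjustment may remove part of the selection, but SAP 5.5 offers it for chance imbalance and precision, not for selection on testing.

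Finally, item 5.1 allows several answers, so a negative client may buy an ACT and a painkiller. The description is therefore not a perfect complement of the label. This adds to the ambiguity.

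**Conclusion.** The concern holds on both counts. The test-negative row contradicts its label, its neighbours and Protocol 7.1. SAP 4.2 and Protocol 7.4 order between-arm models for four outcomes conditioned on a post-randomisation choice that the prices are meant to change.

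The textual findings are certain. The sizes are illustrations that rest on planned uptake, no deterrence by a higher subsidy, and assumed purchase rates by client type. The bias is zero among untested clients if induced testers behave like never-testers. It is zero in the tested groups if induced testers behave like always-testers and, for *Appropriate ACT use*, also have equal positivity. Only secondary outcomes are affected; the primary outcome, its tests and the sample size stand.

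**What to change.** 1. Redefine the row as buying an ACT after a negative RDT (yes/no), or rename it as non-purchase. Either is valid. State how a client who buys both an ACT and another drug is scored. Align Protocol section 4 and SAP *Appropriate ACT use* on whether a negative client who buys nothing counts as adherent.
2. Limit the SAP 4.2 sentence and Protocol 7.4 to outcomes defined on everyone randomised. Report the four conditional outcomes descriptively by arm, for which shell B2 already has the rows, or label any modelled RR as a non-causal comparison.
3. State, before unblinding, that untested clients score no on *Targeted ACT use*, or state another rule, and use it as the randomised secondary comparison. Purchase of a regular-price ACT without a test (Protocol section 4) could also be defined on all randomised clients.

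The cost is wording in two documents; items 4.1, 4.3 and 5.1 already supply the data. The trade-offs are that no causal RR is reported within test groups, and that *Targeted ACT use* largely tracks uptake and so adds limited information.

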### 3.3 Additional Variables of Interest

Variable	Description	Variables and Source	Specifications
Patient gender			Binary: Male/Female
Patient age			Continuous
Household size			Continuous
Highest level of education completed			Categorical: None, Pre-primary, Some Primary, Finished Primary, Some Secondary, Finished Secondary, Some Post-secondary, Finished Post-secondary, Other
Occupation			Categorical: Agricultural, Paid employee, Self-employed (Not in agriculture), Informal employment, Student, Homemaker/Housewife, Not available to work, Unemployed, Others
Wealth category			Binary: under poorest 40 th centile or not

Seriousness of disease			Categorical: Not very serious/minor, Moderate, Very serious
Duration of symptoms			Continuous

## 4 Statistical Analysis Plan

### 4.1 Demographic and Clinical Characteristics (“Table 1”)

We will use principle components analysis to define a wealth index. No significance tests will be performed to test for differences at baseline. Descriptive statistics for continuous variables will include the mean, standard deviation, median, range and the number of observations. Categorical variables will be presented as numbers and percentages.

### 4.2 Analyses Plan for Aim 1

As per the assumptions used in our sample size calculations (see section 2.4), we anticipate there will be no significant interaction effect between RCT and conditional ACT subsidy levels. However, we will evaluate this assumption to protect our analysis from an unexpected interaction effect. Since the assumption of no interaction effect was in terms of risk differences (see Table 1), the test for interaction will also be performed on the absolute scale, though the primary effect measure of interest is the relative risk ratio (RR) and the test results of interaction effect may differ on different scales. If there is no significant interaction effect as expected, we will report the average effect for each of RDT subsidy and conditional ACT subsidy on the proportion of testing uptake on the relative scale. In the unlikely case that a significant interaction effect is detected, we will report the effect of each factors conditional on the other on the relative scale (see Table 3). In either case, adjustment for familywise Type 1 error rate is necessary for multiple hypothesis tests. In our sample size justification (section 2.4) we used a conservative Bonferroni correction; however, in practice, we will use an alpha allocation strategy that splits a 5% Type 1 error rate across our tests in a manner that reflects the a priori importance of each test and provides more power to detect the expected effect sizes. As mentioned previously, the primary effect measure is on the relative scale. However, due to the nature of the model, interpretable relative risk ratios cannot be derived for the average effects. Instead, approximation of the relative risk ratios on log scale will be reported. Different coding methods will not solve this problem, but we choose to use effect coding over dummy coding because effect coding, with the orthogonality property, allows for interpretable main effects

regardless of the presence of an interaction effect. Details of the statistical analysis are as follows.

In our analysis, we will fit a modified Poisson regression model with log link to estimate risk ratios as the primary effect measure (i.e. an effect measure on the relative scale, see Model 1) [2, 3]. Such an approach assumes a Poisson distribution for the binary outcome and then 'fixes' the estimated standard errors to correct for model misspecification (i.e. using a Poisson rather than binomial model). It is the preferred modelling approach to estimate RRs as it avoids some of the convergence issues that may be encountered when using the alternative log-binomial regression approach whilst maintaining good statistical properties. In addition, we will fit a modified Poisson regression model with identity link to estimate risk differences as the secondary effect measure (see Model 2), since the assumption of no interaction effect is made on the absolute scale. However, the optimization decision will be based the primary model (i.e. on the relative scale). All analyses will be based on the intention-to-treat principle whereby all clients will be included in the analysis irrespective of whether they complied with the intervention.

The models will have the following form:

$$\text{Model 1: } \log(E(Y_{ij})) = \beta_0 + \beta_1 \text{RDT\_SUBSIDY\_50\%}_{ij} + \beta_2 \text{ACT\_SUBSIDY\_100\%}_{ij} + \beta_3 \text{RDT\_SUBSIDY\_50\%}_{ij} * \text{ACT\_SUBSIDY\_100\%}_{ij} + \mathbf{w}_{ij} \boldsymbol{\alpha}$$

$$\text{Model 2: } E(Y_{ij}) = \beta_0 + \beta_1 \text{RDT\_SUBSIDY\_50\%}_{ij} + \beta_2 \text{ACT\_SUBSIDY\_100\%}_{ij} + \beta_3 \text{RDT\_SUBSIDY\_50\%}_{ij} * \text{ACT\_SUBSIDY\_100\%}_{ij} + \mathbf{w}_{ij} \boldsymbol{\alpha}$$

where  $Y_{ij}$  is an indicator of whether client  $j$  in outlet  $i$  ( $j=1, \dots, 84$ ;  $i = 1, \dots, 10$ ), chose to get tested for malaria in the retail outlet ( $=1$  if tested,  $0$  otherwise) and  $E(Y_{ij})$  is its expected value.  $\text{RDT\_SUBSIDY\_50\%}_{ij}$  is an indicator for whether the client received the lower RDT price of \$0.20 ( $=1$  if they received the offer of an RDT at \$0.20,  $=-1$  if they received the offer of an RDT at \$0.40) and  $\text{ACT\_SUBSIDY\_100\%}_{ij}$  is an indicator for whether the client received the higher ACT subsidy ( $=1$  if ACT price conditional on a positive test is \$0,  $=-1$  if ACT price conditional on positive test is \$0.40). Therefore,  $\text{RDT\_SUBSIDY\_50\%}_{ij} * \text{ACT\_SUBSIDY\_100\%}_{ij}$  represents an interaction term for clients who receive both the higher RDT and ACT subsidies or both the lower RDT and ACT subsidies ( $=1$  in two situations: a. RDT is offered at \$0.20 and ACT is offered at \$0 conditional on a positive test or b. RDT is offered at \$0.40 and ACT price conditional on positive test is \$0.40,  $=-1$  otherwise).  $\mathbf{w}_{ij}$  is a vector of potential confounder variables (e.g., age, gender, wealth, education) to account for possible imbalances between study arms. To account for possible clustering due to multiple individuals being randomized within 10 different (randomly-sampled) outlets we will use a generalized estimating equations (GEE) approach with

exchangeable working covariance matrix, robust standard errors (to correct for model misspecification due to specifying a Poisson distribution) and finite-sample correction (to obtain unbiased standard errors estimates using the Kauermann-Carroll method)[4, 5]. Regression diagnostics, including residual plots, will be used to verify model assumptions. Because all secondary outcomes are binary, we will use the same modelling approach to compare these outcomes.

In the primary model (Model 1),  $\beta_0$  represents the overall mean of log-mean level (i.e. log-proportion) of testing uptake across all treatment arms.  $\beta_1$  represents the deviation of the log-proportion of testing uptake from the overall mean when reducing the price of the RDT from \$0.40 to \$0.20, averaged across ACT subsidy levels, while  $\beta_2$  represents the deviation of the log-proportion of testing uptake from the overall mean when reducing the price of the ACT, conditional on a positive test, from \$0.40 to \$0, averaged across RDT subsidy levels.  $\beta_3$  represents the interaction effect between the two price changes: it is the additional effect on log-proportion of testing uptake when both commodities are offered at the lower price level or higher price level, and also the negative additional effect if only one of RDT and ACT is offered at a lower price level. Relative risk ratio for the average effect of each of the price reductions cannot be obtained due to the nature of the model. However, an approximation of it can be obtained by exponentiating the parameters and deriving corresponding 95% confidence intervals.

In the secondary model (Model 2),  $\beta_0$  represents the overall mean of the proportion of testing uptake across all treatment arms.  $\beta_1$  represents the deviation of the proportion of testing uptake from the overall mean when reducing the price of the RDT from \$0.40 to \$0.20, averaged across ACT subsidy levels, while  $\beta_2$  represents the deviation of the proportion of testing uptake from the overall mean when reducing the price of the ACT, conditional on a positive test, from \$0.40 to \$0, averaged across RDT subsidy levels.  $\beta_3$  represents the interaction effect between the two price changes: it is the additional effect on the proportion of testing uptake when both commodities are offered at the lower price level or higher price level, and also the negative additional effect if only one of RDT and ACT is offered at a lower price level. Absolute risk differences and corresponding 95% confidence intervals can be obtained by directly evaluating the model parameters.

Our two primary goals are to determine whether RDT uptake increases significantly when the price of the RDT is reduced from \$0.40 (no subsidy) to \$0.20 (a 50% subsidy), averaged over the ACT price levels (i.e. the main effect), and when the price of the ACT conditional on a positive test is reduced from \$0.40 to \$0 (67% subsidy vs 100% subsidy), averaged over the RDT price levels (i.e. the main effect). That is, we wish to test for the main effects of these two commodities. These can be evaluated by testing the null hypotheses  $H_0: 2\beta_1=0$  and  $H_0: 2\beta_2=0$ , with 2% Type 1 error rate respectively. Although, a priori, we hypothesized no statistical interaction

on absolute scale in our sample size calculations, a secondary aim is to determine whether the effect of each of the price changes depends on the price of the other commodity. This can be tested by evaluating the null hypothesis  $H_0: \beta_3=0$  in model 2 on the absolute scale with 1% Type 1 error rate. If this effect is statistically different from zero, we will report the effect of the price reductions of each commodity conditional on the price of the other commodity, with a Type 1 error rate of 1% respectively. If, however, as we expect, there is no statistically significant or scientifically meaningful interaction (i.e.  $\beta_3$  is close to zero), we will estimate the average effects from a model with interaction to match the study design with a Type 1 error rate of 2% respectively. The allocation of Type 1 error rate is based on the a priori importance of the hypothesis tests and provides more power than the conservative strategy employed in our sample size calculations (section 2.4). Contrasts of interest are summarized in Table 3.

In the unlikely case that the modified Poisson models fail to converge, we will use a logit-link in order to estimate odds ratios as the measure of effect. As mentioned before, we will additionally provide estimates of absolute effects (risk differences) in order to provide an intuitive measure of the potential public of the interventions. Such an approach is recommended by the CONSORT statement on reporting of cluster randomized trials [6]. These risk differences will be estimated by changing the log-link to an identity link. If convergence is not achieved, we will consider an alternative specification using a normal distribution with identity link and the same approach of using robust standard errors to account for model misspecification. We will fit all models using Stata version 15 [7].

Table 3: Contrasts of interest	Population	Contrast	Alpha
Interaction effect			
(0a) The interaction effect of RDT subsidy and conditional ACT subsidy.	Full cohort	$2\beta_3$ in Model 2	0.01
Primary outcomes (given no significant interaction effect)			
(1a) Effect of RDT subsidy on the uptake of testing, averaged over the ACT price levels.	Full cohort	$2\beta_1$ in Model 1	0.02
(1b) Effect of conditional ACT subsidy on the uptake of testing, averaged over the RDT price levels.	Full cohort	$2\beta_2$ in Model 1	0.02
Primary outcomes (given strong interaction effect)			
(2a) Effect of RDT subsidy on the uptake of testing, given no conditional ACT subsidy.	No conditional ACT subsidy	$2\beta_1-2\beta_3$ in Model 1	0.01

(2b) Effect of RDT subsidy on the uptake of testing, given conditional ACT subsidy.	Conditional ACT subsidy	$2\beta_1+2\beta_3$ in Model 1	0.01
(2c) Effect of conditional ACT subsidy on the uptake of testing, given no RDT subsidy.	No RDT subsidy	$2\beta_2-2\beta_3$ in Model 1	0.01
(2d) Effect of conditional ACT subsidy on the uptake of testing, given RDT subsidy.	RDT subsidy	$2\beta_2+2\beta_3$ in Model 1	0.01

